8. BIOMARKERS

8.1 Urine Biomarkers

8.1.1 Urine Biomarkers Measurements and Collection Schedule

Urine will be collected over 24-hour periods for urine BoE measurements, during the clinic visits at the end of Weeks -1, 2 and 6. The urine samples collected during a single 24-hour period will be pooled together and weighed. The total weight of all urine collected over each 24 hour period will be documented. Concentrations of the following biomarkers will be measured: total NNAL, total NNN, 3-HPMA, S-PMA, 1-OHP, and Tneq. Creatinine in urine will also be measured and used to report BoE as amount per unit of creatinine.

8.1.2 Bioanalytical Method

Urine concentrations will be determined using validated analytical methods at Celerion Bioanalytical Services, Lincoln, NE and Celerion, Switzerland.

Urine nicotine, cotinine, *trans*-3'-hydroxycotinine, nicotine-*N*-glucuronide, cotinine-*N*-glucuronide, *trans*-3'-hydroxycotinine-*O*-glucuronide, NNN, NNAL, 1-OHP, and creatinine concentrations will be analyzed by liquid chromatography-tandem mass spectrometry (LC-MS/MS) methods at Celerion, Lincoln, NE using validated analytical methods with appropriate quality controls according to applicable portions of Celerion Standard Operating Procedures which were written based on the FDA Guidance for Industry: Bioanalytical Method Validation (May, 2001) and the FDA Good Laboratory Practice regulations (Title 21 CFR Part 58).

Approximate lower limit of quantitation (LLOQ) values for each analyte are shown in the table below. LLOQs will be reported out to the most current validation data and included in the bioanalytical report.

Analyte	LLOQ
Nicotine	50.0 ng/mL
Cotinine	50.0 ng/mL
trans -3'-hydroxycotinine	50.0 ng/mL
Nicotine- N -glucuronide	50.0 ng/mL
Cotinine- N -glucuronide	200 ng/mL
trans -3'-hydroxycotinine- O -glucuronide	200 ng/mL
NNN	0.200 pg/mL
NNAL	5.00 pg/mL
1-OHP	10.0 pg/mL
Creatinine	120 μ g/mL (effective LLOQ)

Urine nicotine, cotinine, *trans*-3'-hydroxycotinine, nicotine-*N*-glucuronide, cotinine-*N*-glucuronide, *trans*-3'-hydroxycotinine-*O*-glucuronide, NNN, NNAL, 1-OHP, and creatinine concentrations will be determined using validated analytical methods at Celerion, Lincoln, NE and Celerion, Switzerland.

Urine 3-HPMA and S-PMA concentrations will be analyzed by LC-MS/MS methods at Celerion, Switzerland. The analysis will be performed according to the standards described in the Swiss Ordinance relating to Good Laboratory Practice, adopted 18 May 2005 [RS 813.112.1]. This Ordinance is based on the OECD Principles of Good Laboratory Practice, as revised in 1997 and adopted 26 November 1997 by decision of the OECD Council [C(97)186/Final]. The OECD Principles of Good Laboratory Practice are accepted by Regulatory Authorities throughout the European Union, the United States of America and Japan. In addition, the analysis of clinical trial samples will be conducted in accordance with the relevant standards of Good Clinical Practice and Standard Operating Procedures based on the recommendations of the EMA 'Reflection paper for laboratories that perform the analysis or evaluation of clinical trial samples' (EMA/INS/GCP/532137/2010), the EMA 'Guideline on bioanalytical method validation' (EMEA/CHMP/EWP/192217/2009) and the FDA 'Guidance for Industry, Bioanalytical Method Validation', (U.S. Department of Health and Human Services, Food and Drug Administration, CDER, CVM, May 2018).

Approximate LLOQ values for each analyte are shown in the table below. LLOQs will be reported out to the most current validation data and included in the bioanalytical report.

Analyte	LLOQ
3-HPMA	20 ng/mL
S-PMA	0.025 ng/mL

8.1.3 Urine Biomarkers Analysis

The following variables will be determined for each urine biomarker at each collection week:

- Measured concentration
- Total biomarker mass excreted per 24 hours (primary analysis variable)
- Total mass excreted per 24 hours absolute change from Baseline
- Total mass excreted per 24 hours percent change from Baseline
- Creatinine-normalized excretion level
- Creatinine-normalized change from baseline
- Creatinine-normalized percent change from baseline

Nicotine equivalents will be calculated as the molar sum of nicotine, cotinine, trans 3'hydroxycotinine and their glucuronides excreted in urine over 24 hours:

The concentration of each metabolite will first be multiplied by the 24-hour urine volume to obtain the total amount excreted in 24 hours, then divided by the molecular weight of the metabolite to obtain the total amount of each in moles. The sum in moles will then be converted to Tneq by multiplying by the molecular weight of nicotine.

Nicotine (mg/24h)	= nicotine concentration [ng/mL] × 24h urine volume [mL] ÷ 1000 000
Nicotine-glucuronide (mg/24h)	= nicotine glucuronide concentration [ng/mL] × 24h urine volume [mL] ÷ 1000 000
Cotinine (mg/24 hours)	= cotinine concentration [ng/mL] × 24h urine volume [mL] ÷ 1000 000
Cotinine-glucuronide (mg/24h)	= cotinine glucuronide concentration [ng/mL] × 24h urine volume [mL] ÷

		1000 000
Trans-3'-hydroxycotinine (mg/24h)	=	trans-3'-hydroxycotinine concentration [ng/mL] × 24h urine volume [mL] ÷ 1000 000
Trans-3'-hydroxycotinine-glucuronide (mg/24h)	=	trans-3'-hydroxycotinine glucuronide concentration [ng/mL] × 24h urine volume [mL] ÷ 1000 000
Nicotine equivalents (mg/24 hours)	=	(nicotine [mg/24h]/162.23 [mg/mmol] + nicotine-gluc [mg/24h]/338.36 [mg/mmol] + cotinine [mg/24h]/176.22 [mg/mmol] + cotinine-gluc [mg/24h]/352.34 [mg/mmol] + trans-3'- hydroxycotinine [mg/24h]/192.22 [mg/mmol] + trans-3'- hydroxycotinine-gluc [mg/24h]/368.34 [mg/mmol]) x 162.23 (mg/mmol)

Urine biomarker concentration values reported as below the limit of quantitation (BLQ) will be set to one-half of the limit of quantitation prior to calculating the 24-hour mass excreted or Tneq. Total urine weight (g) will be collected during the study and converted to urine volume using the assumed density of 1 gram (g) equals 1 milliliter (mL).

Creatinine-adjusted concentrations will be calculated as shown in [Section 8.1.4](#). Absolute and percent change from baseline will be calculated as shown in [Section 8.1.5](#).

8.1.4 Creatinine Adjusted Urine Biomarker Concentrations

Creatinine concentrations will be used to adjust the concentration values of all urine biomarkers (Total NNAL, total NNN, 3-HPMA, S-PMA, 1-OHP, and Tneq) as follows:

$$\text{Urine biomarker (mass/mg creatinine)} = \frac{\text{urine biomarker (mass/mL)} \times 100}{\text{creatinine (mg/dL)}}$$

8.1.5 Change from Baseline Urine Biomarker Concentration

Urine biomarker change from baseline on Weeks 2 and 6 will be calculated as follows, where Baseline = Week -1:

$$\text{Absolute change from baseline} = \text{Post Product Use Value} - \text{Baseline Value}$$

Percent change from baseline (%) = (Post Product Use Value – Baseline Value) / Baseline Value x 100 %

8.2 Blood Biomarkers

8.2.1 Blood Biomarkers Measurements and Collection Schedule

Blood samples for COHb in whole blood and cotinine in plasma will be collected on Weeks -1, 2, and 6. Samples will be collected at approximately 13:00, following the subject's lunchtime meal, and will be preceded by at least a 30 minute abstention from study product use.

8.2.2 Bioanalytical Method

Whole blood COHb and plasma cotinine will be analyzed by spectrophotometric measurement and LC-MS/MS, respectively, at Celerion Bioanalytical Services, Lincoln, NE, using validated analytical methods with appropriate quality controls according to applicable portions of Celerion Standard Operating Procedures which were written based on the FDA Guidance for Industry: Bioanalytical Method Validation (May, 2001) and the FDA Good Laboratory Practice regulations (Title 21 CFR Part 58). The LLOQ for COHb will be 0.2%. The LLOQ for plasma cotinine will be 1.00 ng/mL.

8.2.3 Blood Biomarkers Analysis

Absolute and percent change from baseline in blood biomarkers will be calculated as described for urine in [Section 8.1.5](#).

8.3 Data Summarization and Presentation of Biomarkers of Exposure

Blood biomarker concentrations, urine biomarker concentrations, urine creatinine concentrations, and the creatinine-adjusted urine biomarker concentrations will be listed by product, subject and week for all biomarkers. All BLQ values will be presented as “BLQ” in the listings.

Blood biomarker concentrations, blood biomarker absolute change from baseline and blood biomarker percent change from baseline as well as urine biomarker mass excreted per 24 hours, absolute change from baseline, percent change from baseline of total mass excreted per 24 hours, creatinine-normalized excretion level, creatinine-normalized excretion absolute change from baseline, and creatinine-normalized excretion percent change from baseline will be summarized by product group and week for all biomarkers using descriptive statistics (n, mean, SD, CV%, SEM, minimum, median, and maximum). The descriptive statistics will be presented for both PP and ITT populations.

8.4 Statistical Analysis of Biomarkers of Exposure

Paired t-tests will be used to compare urinary NNAL, NNN, 3-HPMA, S-PMA, 1-OHP, Tneq mass excreted, and blood COHb measures at the Week 2 and 6 time points with the baseline (Week -1) values. This analysis will be conducted on the evaluable subjects in the PP population. If data are unexpectedly found not to be normally distributed, an appropriate non-parametric test will be performed.

Differences will be considered statistically significant at an alpha level of 0.05. The same SAS codes used in [Section 7.3](#) for paired t-test will be used for the analysis.

In addition, a linear mixed model analysis of variance will be used to compare the between product group differences in the absolute change from baseline values of each of the urinary and blood BoEs. The same statistical model and SAS codes used in [Section 7.3](#) for product group comparisons will be used for the analysis.

9. PHARMACOKINETIC ANALYSIS

9.1 Measurements and Collection Schedule

For a randomly-selected subset of 12 non-menthol and 12 menthol smoker subjects, PK blood sampling will occur following the completion of the 24-hour urine collection period on clinic visits at Weeks -1, 2, and 6. The selected subjects will remain in the clinic for a further night, in which they will abstain from smoking any cigarettes/using any nicotine-containing products for at least 12 hours prior to the PK assessment session. During this session, subjects will smoke a single cigarette (either their UB on Week -1 or the VLN on Weeks 2 and 6) *ad libitum* during a 5-minute period. Serial blood samples will be collected for plasma nicotine analysis at 5 minutes prior to and at 2, 5, 7, 10, 12, 15, 20, 30, 45, 60, 90, 120, 150, and 180 minutes relative to the start of cigarette smoking.

All concentration data will be included in the calculation of the individual PK parameters, the individual concentration-time plots (based on actual sample times), and in the mean concentration-time plots (based on nominal sample times). However, if there are any significant deviations from nominal sample times, some concentration data may be excluded from mean concentration-time plots and/or additional concentration-time plots of the mean data may be provided. All deviations and excluded data will be provided and discussed in the CSR.

9.2 Bioanalytical Method

Plasma concentrations of nicotine will be determined using a LC-MS/MS method at Celerion Bioanalytical Services, Lincoln, NE, using a validated analytical method with appropriate quality controls according to applicable portions of Celerion Standard Operating Procedures which were written based on the FDA Guidance for Industry: Bioanalytical Method Validation (May, 2001) and the FDA Good Laboratory Practice regulations (Title 21 CFR Part 58). The analytical range (LLOQ

– upper limit of quantitation [ULOQ]) for nicotine is expected to be 0.200 – 25.0 ng/mL.

9.3 NonCompartmental Pharmacokinetic Analysis and Parameter Calculation

9.3.1 Plasma Nicotine Pharmacokinetic Parameters

The appropriate noncompartmental PK parameters will be calculated from the plasma nicotine concentration-time data using Phoenix[®] WinNonlin[®] Version 7.0 or higher. Actual sample times will be used in the calculations of the PK parameters. Concentration data will be presented: 1) unadjusted for baseline and 2) baseline-adjusted. The baseline is the plasma nicotine concentration value obtained before the start of cigarette smoking (-5 minutes) and the adjustment will be subject-specific. For the calculation of PK parameters, plasma nicotine concentrations below the limit of quantification (BLQ) will be set to one-half (½) the LLOQ. All PK parameters included in the protocol are listed in Table 6.1 below, and are defined as appropriate for study design.

Table 6.1. Noncompartmental Pharmacokinetic Parameters to be Calculated

Parameter	Definition	Method of Determination
AUC0-180	Area under the concentration-time curve from time 0 to 180 minutes	Calculated using the Linear Trapezoidal with Linear Interpolation Method
Cmax	The maximum observed concentration	Taken directly from bioanalytical data
Tmax	The time to reach Cmax	Taken from the concentration versus time data as the actual time corresponding to the maximum observed concentration

For the calculation of PK parameters, subjects must have at least 3 postproduct use data points. If the preproduct data point is missing then a value of ½ the LLOQ will be imputed. Subjects for whom there are insufficient data to calculate the PK parameters will be included in the concentration tables only.

Baseline adjustment

For PK parameters calculated using the baseline-adjusted concentrations, adjustment will be done using the reported nicotine half-life of 120 minutes (elimination rate constant, $\lambda z = 0.0058 \text{ min}^{-1}$) with the following equation:

$$C_{t(\text{adj})} = C_t - C_0 \times e^{-\lambda z \times t}$$

where $C_{t(\text{adj})}$ is adjusted concentration, C_t is observed concentration, C_0 is the concentration at the pre-product use time point, t is actual sampling time since product administration, and t_1 is the actual sampling time since pre-product administration sample time.

After correction for pre-product use values, some concentrations may be BLQ and some may be negative values. All values obtained will be reported as is even if these values are BLQ or negative. Negative values will be assigned a value of zero in summary statistics and for PK parameter calculations.

9.4 Data Summarization and Presentation of PK Concentrations and Parameters

All nicotine PK concentrations and/or PK parameters descriptive statistics will be generated using SAS[®] and/or Phoenix[®] WinNonlin[®] as appropriate.

The plasma concentrations of nicotine will be listed by subject and summarized by study product group, time point and sex for all subjects in the PK Population. Plasma concentrations of nicotine will be presented with the same level of precision as received from the bioanalytical laboratory. Summary statistics, including n, Mean, SD, CV%, SEM, minimum, median, and maximum will be calculated for all nominal concentration time points. Excluded subjects will be included in the concentration listings, but will be excluded from the summary statistics and noted as such in the tables. All BLQ values will be presented as “BLQ” in the concentration listings and footnoted accordingly. The descriptive statistics will be presented for the PK population in both PP and ITT populations.

Mean and individual concentration-time profiles will be presented on a linear scale and semi-log scale. Linear profiles will be presented with and without SD.

Plasma nicotine PK parameters will be listed and summarized by study product group and sex for all subjects in the PK Population (from ITT and PP populations).

Pharmacokinetic parameters will be reported to 3 significant figures for individual parameters, with the exception of T_{max} , which will be presented with 2 decimal places. Summary statistics (n, Mean, SD, CV%, SEM, minimum, median and maximum), will be calculated for plasma nicotine PK parameters AUC0-180, Cmax and T_{max} . In addition, geometric mean (Geom Mean) and geometric CV% (Geom CV%) will be calculated for AUC0-180 and Cmax. Excluded subjects will be listed in the PK parameter tables, but will be excluded from the summary statistics and noted as such in the tables. The descriptive statistics will be presented for the PK population in both PP and ITT populations.

The level of precision for each concentration and PK parameter statistic will be presented as follows: minimum/maximum in same precision as bioanalytical data/PK parameter, mean/median in one more level of precision than minimum/maximum, SD in one more level of precision than mean/median, n will be presented as an integer and CV% will be presented to the nearest tenth.

9.5 Statistical Analysis of PK Parameters

Paired t-tests (on AUC and Cmax) will be used to compare baseline adjusted nicotine PK parameters at the Week 2 and 6 time points with the baseline (Week -1) values. This analysis will be conducted on subjects in the PK population (from the PP population only). If data are unexpectedly found not to be normally distributed, an appropriate non-parametric test will be performed. Differences will be considered statistically significant at an alpha level of 0.05. Geometric means, geometric mean ratio (GMR), 90% confidence interval for GMR, and p-value will be presented. The analysis is based on the log-transformed data. The same SAS codes used in [Section 7.3](#) for paired t-test will be used for the analysis.

10. SUBJECTIVE EFFECTS

10.1 Measurements and Collection Schedule

The FTCD, QSU-Brief, MNWS-R, perceived health risk scale will be completed at the end of each clinic visit, at the end of Weeks -1 (Baseline), 2, 4 and 6.

10.2 Data Summarization and Presentation of Subjective Effects

10.2.1 Analysis variables

Total score for FTCD will be calculated for each subject at each time point and used as the analysis variable for FTCD questionnaire

The factor scores for QSU-brief: Responses will be used for the QSU-brief questionnaire. There are two factor scores: Factor 1 ('anticipation of pleasure from smoking' calculated as the average of the response scores from Questions 1, 3, 6, 7, and 10) and Factor 2 ('relief of nicotine withdrawal' calculated as the average of the response scores from Questions 2, 4, 5, 8, and 9).

Total score for MNWS-R (calculated as the sum of the responses for each question) will be used as the analysis variable for MNWS-R questionnaire.

Response for perceived health risk scale will be used as the analysis variable.

Questionnaire answers will be listed by subjects for each questionnaire. Change from baseline will be calculated for each post-baseline time point for the analysis variables. All data will be listed by subject and summarized by time point using descriptive statistics. The descriptive statistics will be presented for both PP and ITT populations.

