1.2 Study Purpose

The purpose of this study is to examine whether measures of cigarette consumption behavior (cigarettes per day and smoking topography) are changed when smokers switch from smoking conventional cigarettes to smoking cigarettes with a very low nicotine (VLN) content (0.4 mg nicotine per gram of tobacco). A secondary purpose is to examine changes in BoE, nicotine pharmacokinetics and subjective measures of dependence, smoking urges, withdrawal symptoms and perceived health risks, when subjects switch to smoking VLN cigarettes.

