5.10 Product Trial

At screening, subjects will have an opportunity to smoke 2-3 VLN cigarettes over a 1-hour period to ensure that they can tolerate smoking those cigarettes for a period of 6 weeks. The number of cigarettes smoked will be documented, as will any abnormal events (e.g., excessive coughing) during the product trial. Subjects who react negatively (*i.e.*, unwilling to use and/or cannot tolerate the product [experience adverse events (AEs) that will prevent them from continuing to use the product as judged by the Investigator]) to the VLN cigarettes during the product trial period will not continue in the study.

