APPENDIX 3: Minnesota Nicotine Withdrawal Scale - Revised (MNWS-R)

Please rate yourself for the last day

Scale: 0 = none, 1 = slight, 2 = mild, 3 = moderate, 4 = severe

1. Angry, irritable, frustrated	0	1	2	3	4
2. Anxious, nervous	0	1	2	3	4
3. Depressed mood, sad	0	1	2	3	4
4. Desire or craving to smoke	0	1	2	3	4
5. Difficulty concentrating	0	1	2	3	4
6. Increased appetite, hungry, weight gain	0	1	2	3	4
7. Insomnia, sleep problems, awakening at night	0	1	2	3	4
8. Restless	0	1	2	3	4
9. Impatient	0	1	2	3	4
10. Constipation	0	1	2	3	4
11. Dizziness	0	1	2	3	4
12. Coughing	0	1	2	3	4
13. Dreaming or nightmares	0	1	2	3	4
14. Nausea	0	1	2	3	4
15. Sore throat	0	1	2	3	4

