10.3 Statistical Analysis of Subjective Effects

Paired t-tests will be used to compare subjective effects measures at the Week 2 and 6 time points with the baseline (Week -1) values. This analysis will be conducted on the evaluable subjects in the PP population. If data are unexpectedly found not to be

normally distributed, an appropriate non-parametric test will be performed. Differences will be considered statistically significant at an alpha level of 0.05. The same SAS codes used in [Section 7.3](#) for paired t-test will be used for the analysis.

In addition, a linear mixed model analysis of variance will be used to compare the between product group differences in the absolute change from baseline values of each of the urinary and blood BoEs. The same statistical model and SAS codes used in [Section 7.3](#) for product group comparisons will be used for the analysis.

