Appendix 16.2.6.14 MNWS-R Response and Total Score (Safety Population)

Subject Number	Product Group	Study Week	Date	Question*															Total Score
				1	2	3	4	5	6	7	8	9	10	11	12	13	14	15	
X	XX	-1	DDMMYYYY	XXX	XXX	XXX	XXX	XXX	XXX	XXX	XXX	XXX	XXX	XXX	XXX	XXX	XXX	XXX	

Note: *1. Angry, irritable, frustrated; 2. Anxious, nervous; 3. Depressed mood, sad; 4. Desire or craving to smoke
5. Difficulty concentrating; 6. Increased appetite, hungry, weight gain; 7. Insomnia, sleep problems, awakening at night;
8. Restless; 9. Impatient; 10. Constipation; 11. Dizziness; 12. Coughing; 13. Dreaming or nightmares; 14. Nausea; 15. Sore throat
Scale: 0 = none, 1 = slight, 2 = mild, 3 = moderate, 4 = severe

Subjects used their own usual brand cigarettes at Week -1.

VLN non-mentholated = Non-mentholated VLN cigarettes

VLN mentholated = Mentholated VLN cigarettes

UB non-mentholated = Subjects' UB non-mentholated filtered cigarettes

UB mentholated = Subjects' UB mentholated filtered cigarettes

Program: /CAXXXX/sas_prg/stsas/lis_PROGRAMNAME.sas DDMMYYYY HH:MM

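### The only analysed withdrawal score (15-item MNWS-R total) includes coughing and sore throat, so airway effects of changing cigarette could move it without any change in withdrawal

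*SAP*

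**What the plan says.** For the MNWS-R, SAP 10.2.1 states: "Total score for MNWS-R (calculated as the sum of the responses for each question) will be used as the analysis variable". The form in Protocol Appendix 3 prints 15 items under one response key, "Scale: 0 = none, 1 = slight, 2 = mild, 3 = moderate, 4 = severe", and its last item is "15. Sore throat". The listing shell in SAP Appendix 16.2.6.14 repeats the items; the final six are "10. Constipation; 11. Dizziness; 12. Coughing; 13. Dreaming or nightmares; 14. Nausea; 15. Sore throat". The questionnaires serve the secondary purpose in Protocol 1.2, which covers "subjective measures of dependence, smoking urges, withdrawal symptoms and perceived health risks". The MNWS-R is the instrument for withdrawal symptoms.

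SAP 10.3 sets the test: "Paired t-tests will be used to compare subjective effects measures at the Week 2 and 6 time points with the baseline (Week -1) values". It is run in the per-protocol population, and "Differences will be considered statistically significant at an alpha level of 0.05". The between-group paragraph of SAP 10.3 names the biomarkers rather than the questionnaires, but SAP 13.2 lists a between-group table for the MNWS-R total (Table 14.2.9.3.3), so that comparison is evidently intended.

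All planned MNWS-R tables (11-26, 11-27 and the 14.2.9.3 series) use the total. Individual item responses appear only in the by-subject listing. In the same section the QSU-Brief is divided into two factor scores; the MNWS-R has no such division.

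Protocol 5.10 has sites document "any abnormal events (e.g., excessive coughing) during the product trial", the hour at screening in which subjects smoke 2 to 3 VLN cigarettes.

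**The concern.** Switching changes two things at once: the nicotine delivered and the cigarette itself. A withdrawal score should respond to the first. Coughing and sore throat could respond to the second, and they enter the total with the same weight as irritability or restlessness.

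The error could run either way. If VLN smoke irritates the airway more than the usual brand, the total rises and looks like withdrawal. If subjects smoke less, as Protocol 1.3 anticipates, and cough eases as a result, the total falls and can hide a real rise in withdrawal. Protocol 1.1 presents withdrawal symptoms as one indicator of whether low-nicotine cigarettes reduce addiction, so a misread score would bear on that argument. As planned, no tabulated result lets a reader tell these explanations apart.

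**Working it through.** The documents give no power calculation, SD or expected change for the MNWS-R, so there is no planned figure to reproduce. The check covers the weight of the two items, their effect on the score, and how far they could drive the test.

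**1. Weight in the score** (15 items, each 0 to 4, Protocol Appendix 3)

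- Full total: 15 × 4 = 60.
- Items 12 and 15: 2 × 4 = 8, and 8/60 = 13.3%.
- Coughing alone: 4/60 = 6.7%.
- Score without the two items: 13 × 4 = 52.

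**2. Offsetting changes.** The change in the total is the plain sum of the item changes. A one-point fall in coughing with a one-point rise in irritability gives −1 + 1 = 0 on the total, but +1 on the 13-item score.

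**3. Effect on the paired test (illustration).** Suppose the other 13 items do not change on average and the two airway items shift the mean total by d. The probability of a two-sided significant result at 0.05 comes from the noncentral t distribution with n − 1 degrees of freedom and noncentrality (d/SD) × √n. For d = 1.0, SD = 4 and n = 50, the noncentrality is 0.25 × 7.07 = 1.77 and the probability is 0.41.

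Inputs: n = 50 per VLN group (SAP 4.1) and 100 for the combined VLN group used by the SAP 7.3 code that SAP 10.3 adopts, both before per-protocol exclusions. The SD of the change in total score (4 to 10) and the shifts are assumptions; neither is in the documents.

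| Mean shift in total | n | SD 4 | SD 6 | SD 8 | SD 10 |
|---|---|---|---|---|---|
| 0.5 (coughing alone by 0.5) | 50 | 0.14 | 0.09 | 0.07 | 0.06 |
| 0.5 | 100 | 0.24 | 0.13 | 0.10 | 0.08 |
| 1.0 (both items by 0.5) | 50 | 0.41 | 0.21 | 0.14 | 0.11 |
| 1.0 | 100 | 0.70 | 0.38 | 0.24 | 0.17 |
| 2.0 (both items by 1.0) | 50 | 0.93 | 0.64 | 0.41 | 0.28 |
| 2.0 | 100 | >0.99 | 0.91 | 0.70 | 0.51 |

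The test is two-sided, so a fall of the same size gives the same probabilities with the sign reversed. The nominal level is 0.05.

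**4. Does the usual-brand comparison remove it?** Write w for the mean change due to withdrawal and a for an airway shift that occurs only in those who switch. The between-group difference is (w_VLN + a) − w_UB, so a remains in full. The comparison removes only what both groups share.

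**The case against.** The strongest case against acting has five parts.

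- **The protocol does not say that VLN cigarettes provoke cough.** Protocol 5.10 describes a one-hour tolerance check and offers coughing as an example of what to record. Nothing says VLN is harsher than the usual brand. This stands as a limit: coughing is an anticipated possibility, not an established effect. A reader might infer that the protocol treats both coughing and sore throat as VLN reactions. It does not; sore throat appears only as a questionnaire item.
- **Baseline and screening absorb part of it.** Subjects already smoke at Week -1, so existing smoker's cough is in the baseline, and those who cannot tolerate VLN leave after the product trial. This reduces the problem. It does not remove tolerable symptoms that change over six weeks.
- **The effect may be small.** If only coughing moves, by 0.5, the probability of a significant result is 0.06 to 0.14 at n = 50. That is a modest excess over 0.05, and the SDs are assumed.
- **The form is one scale.** Appendix 3 prints 15 items with no subscales. Dropping items may discard real withdrawal signal. This is a good reason to keep the total. It also counts against a stronger reading, that items 10 to 15 (24 of 60 points, 40%) are all contaminated and only items 1 to 9 should be tested. No irritation argument covers constipation, dizziness, dreams or nausea, and nothing in the documents identifies items 1 to 9 as the withdrawal core.
- **Other outputs help.** Item responses are listed by subject, adverse events are tabulated by preferred term (SAP 11.4), and QSU-Brief Factor 2 concerns relief of withdrawal without either item. These let a reader query an odd total, but none gives a summarised or tested MNWS-R result free of the two items.

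**Conclusion.** The concern holds in a limited form. The only analysed withdrawal score contains two airway items worth up to 13.3% of its range, and no planned table separates them. The total could therefore change, or fail to change, for reasons other than withdrawal, and the usual-brand groups do not correct a shift specific to switching.

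A reader might infer that product irritation will be reported as withdrawal. The documents do not support that: they give neither the direction nor the size of any shift, and a fall in cough would hide withdrawal rather than mimic it. The probabilities under working rest on assumed shifts and SDs, and on no change in the other 13 items. They show that distortion is possible over a wide range, not that it is likely. This is a secondary endpoint with no directional hypothesis, so the point is a worthwhile clarification of the analysis, not a threat to the primary result.

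**What to change.** In SAP 10.2.1, before database lock:

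- Keep the 15-item total as planned.
- Prespecify a second MNWS-R score that omits items 12 and 15 (13 items, range 0 to 52), and analyse it with the same paired and between-group tests, as added rows in Tables 11-27, 14.2.9.3.2 and 14.2.9.3.3.
- Summarise items 12 and 15 by product group and visit.
- State that a change in the total will be read as withdrawal only if the 13-item score agrees in direction and test result, and that any disagreement will be reported. Requiring agreement means the second score gives no extra chance of a positive claim.
- Use a narrower core, such as items 1 to 9, only if the sponsor confirms it against the instrument's scoring source.

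The cost is one derived variable, one extra secondary score and a few table rows. No new data are needed. Fixing the item set now also avoids choosing it after the results are known.
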